[name]

Clinical Study Protocol CCP-020 (Diacerein 1%) Topical Ointment Sponsor Protocol No. CCP-020-104 TKL Study No. PB610317

A 4 Day, Randomized Study to Evaluate the Potential of CCP-020 (Diacerein 1%) Topical Ointment to Induce a Phototoxicity Skin Reaction in Healthy Subjects, Using a Controlled Photopatch Test

Author: Document type: Development Phase: Document Date: Document Status Number of Pages:

Clinical Study Protocol 1 23-October-2017 Amendment 1 **38**

Property of **Castle Creek Pharmaceuticals, LLC**. Confidential May not be used, divulged, published, or otherwise disclosed without the consent of **Castle Creek Pharmaceuticals, LLC**.

Synopsis

Study Title:	A 4 Day, Randomized Study to Evaluate the Potential of CCP-020 (Diacerein 1%) Topical Ointment to Induce a Phototoxicity Skin Reaction in Healthy Subjects, Using a Controlled Photopatch Test
TKL Study Number:	PB610317
Sponsor Protocol Number:	CCP-020-104
Sponsor:	Castle Creek Pharmaceuticals, LLC
Development Phase:	1
Study Objectives:	To determine the potential of CCP-020 (Diacerein 1%) Topical Ointment and vehicle ointment to cause irritation when topical application to skin is followed by light exposure.
Study Design:	On Day 1, CCP-020 (Diacerein 1%) Topical Ointment and vehicle ointment will each be applied to 2 sites on the lower thoracic area of the back under fully occlusive patches for approximately 24 (\pm 2) hours. This will be the only application during the study. Minimal erythema dose (MED) irradiation will also be performed for each subject on Day 1. After patch removal on Day 2, all application sites will be evaluated and one application site of each study product will be irradiated with 16 J/cm ² of Ultraviolet A (UVA) followed by 0.5 times the MED of UVA/Ultraviolet B (UVB) irradiation. An additional site will also be irradiated with 16 J/cm ² of UVA followed by 0.5 times the MED of UVA/UVB and will serve as an untreated control. On Day 3, approximately 24 hours (\pm 4 hours) after irradiation and Day 4, approximately 48 hours (\pm 4 hours) after irradiation, all application sites and the untreated control site will be evaluated.
Planned Sample Size:	30 evaluable subjects
Study Population:	Healthy adult male and female volunteer subjects
Investigational Products:	Each study product, CCP-020 (Diacerein 1%) Topical Ointment and vehicle ointment will be applied in an amount of 0.2 mL under occlusive patch conditions to 2 sites (2 cm x 2 cm each) on the infrascapular area of the back once for approximately 24 hours (\pm 2 hours).
Control:	An untreated irradiated non-occlusive (open) control site.
Efficacy Evaluation Criteria:	Not applicable

Castle Creek Pharmaceutica Clinical Study Protocol CCI Date 23-October-2017	ıls, LLC P-020-104	Confidential	Page 3 Protocol PB610317 Amendment 1
Safety Evaluation	Phototoxic completing t	potential of the study products will the study.	l be evaluated for all subjects
	All local a Investigator study produc	nd systemic adverse events (AEs) will be evaluated. The intensity, dura cts are to be rated for all AEs.	observed by or reported to the ation, and causal relationship to the
Statistical Methods:	Selected pair response sco compared a comparisons ointment on Topical Oin irradiated sig	rwise comparisons will be performed o ores in the context of the analyses of re: each test sample irradiated versu s on each side (CCP-020 (Diacerein 1% both the irradiated and non-irradiated a thment versus untreated and vehicle de).	on the mean of the Day 3 and Day 4 E variance (ANOVA). Pairs to be as non-irradiated and all pairwise (6) Topical Ointment versus vehicle sides and CCP-020 (Diacerein 1%) ointment versus untreated on the
Number of Study Centers:	Single Cente	r	
Planned Dates of Study	November 2	017 – December 2017	

Castle Creek Pharmaceuticals, LLC Clinical Study Protocol CCP-020-104 Date 23-October-2017 Confidential

Page 4 Protocol PB610317 Amendment 1

Signature page

Product names: CCP-020 (Diacerein 1%) Topical Ointment Vehicle Ointment

TKL Study number:PB610317Sponsor protocol number:CCP-020-104

The signatures of the representatives on this and the following page constitute their approval of this protocol and provide the necessary assurances that this study will be conducted according to all stipulations stated in the protocol, including all statements as to confidentiality. It is also agreed that the study will not be initiated without the approval of an appropriate Institutional Review Board.

Approved by the following:

Castle Creek Pharmaceuticals, LLC:

Property of Castle Creek Pharmaceuticals, LLC.

Clinical Study Protocol

Confidential

Page 5 Protocol PB610317 Amendment 1

Signature page for the Principal Investigator

1. INTRODUCTION

Because CCP-020 (Diacerein 1%) Topical Ointment is formulated for topical use and has shown to absorb light within the range of natural sunlight (290-400 nm), it is necessary to determine the potential of this product to cause a phototoxic reaction after topical application and irradiation to the skin. This study investigates the phototoxic potential of CCP-020 (Diacerein 1%) Topical Ointment under standardized conditions compared with an untreated control site.

The study will be conducted in compliance with Food and Drug Administration (FDA) regulations, the ethical principles of the Declaration of Helsinki concerning medical research in humans (Recommendations Guiding Physicians in Biomedical Research Involving Human Subjects, Helsinki 1964 and amendments 2013), the International Conference on Harmonization (ICH) – Good Clinical Practice (GCP) Guidelines as currently amended, and all applicable standard operating procedures (SOPs) of TKL Research, Inc. (TKL).

1.1. Background Information

CCP-020 (previously developed as AC-203) is a topical ointment containing diacerein (4,5bis[acetyloxy]-9,10-dihydro-9,10-dioxo-2-anthracene carboxylic acid; also known as diacetylrhein), a highly purified anthraquinone derivative, and is being developed by Castle Creek Pharmaceuticals for the treatment of epidermolysis bullosa simplex (EBS). The capsule formulation of diacerein, intended for oral use and systemic absorption, was initially approved for use in osteoarthritis (OA) in France in 1992 (as Artodar[®], ART50[®], or Zondar[®]). Since then, it has received marketing authorization in over 30 countries in Europe, South America, and Asia. It is classified as a Symptomatic Slow-Acting Drug in OA. Following oral administration of the capsule formulation, diacerein is rapidly metabolized to the deacetylated active metabolite, rhein. Similarly, diacerein in the topical formulation is hydrolyzed to rhein in the epidermis and the dermis following administration. Diacerein and rhein have been shown to inhibit the in vitro and in vivo production and activity of interleukin (IL)-1 β and other proinflammatory cytokines. It has a novel mode of action that differentiates it from non-steroidal anti-inflammatory drugs (NSAIDs) and other conventional forms of drug therapy.

For the development of CCP-020, a total of 10 animal studies have been conducted with CCP-020 ointment 1%, including one skin penetration study, three acute dermal toxicity studies, one phototoxicity study, three pharmacokinetic studies, and two sub-chronic juvenile toxicity studies. CCP-020 was well-tolerated in these studies and no untoward adverse effects (AEs) were noted. To date, two clinical studies of CCP-020 have been completed in patients with epidermolysis bullosa simplex (EBS). These include a Phase one pilot study in five patients and a Phase 2, multiple-site study in 17 patients in Europe. The Phase 2 study demonstrated CCP-020 was well-tolerated and no treatment-related AEs were reported. The Investigator's Brochure should be consulted for summaries of the results of these studies.¹

This Phase 1 study will assess the phototoxicity potential of CCP-020 (Diacerein 1%) topical ointment.

2. STUDY OBJECTIVES

The objective of this study is to determine the phototoxic potential of CCP-020 (Diacerein 1%) Topical Ointment and vehicle ointment when topical application to skin is followed by light exposure.

In addition, safety will be assessed by evaluation of any adverse events (AEs) reported during the study.

3. INVESTIGATIONAL PLAN

3.1. Study Design

This is a single-center, randomized, within-subject comparison study of CCP-020 (Diacerein 1%) Topical Ointment and vehicle ointment. CCP-020 (Diacerein 1%) Topical Ointment and vehicle ointment will each be applied to 2 sites, one which will be irradiated and one which will remain non-irradiated. The irradiated and non-irradiated sites will be compared with each other and with an untreated irradiated control.

A total of 4 application sites (2 cm x 2 cm each) will be marked on the subject's lower thoracic area of the back: 2 sites on each side of the back – 2 sites for CCP-020 (Diacerein 1%) Topical Ointment and 2 sites for vehicle ointment. Each study product will be applied according to the randomization scheme in an amount of 0.2 mL under occlusive patch conditions once during the study.

Approximately 24 (\pm 2) hours post study product application, the patches will be removed by study staff. The sites will then be graded for cutaneous reactions by a trained evaluator and the designated sites, including the untreated site, will be exposed to irradiation. One side of the back will be designated for irradiation and the other side will remain non-irradiated. An additional site will be marked on the "irradiated side" of the back which will receive no treatment, but will receive irradiation to serve as an untreated irradiated control. The sites and control will be examined at approximately 24 and 48 hours post irradiation and graded for reactions. Cutaneous reactions at the application sites will be evaluated using a visual scale that rates the degree of erythema, edema, and other signs of cutaneous irritation (see Table 3 and Table 4).

Safety evaluations include collection of adverse events (AEs).

3.2. Discussion of Design

Results are interpreted according to working criteria which are based upon published works, as well as the clinical experience of TKL Research, Inc. These working criteria are periodically reviewed and amended subject to new information which becomes available.

This phototoxicity study is designed to detect the ability of the CCP-020 (Diacerein 1%) Topical Ointment and vehicle ointment to cause topical skin irritation when exposed to light. Each subject is to receive applications of CCP-020 (Diacerein 1%) Topical Ointment and vehicle ointment to 2 separate sites. One will be irradiated and one will remain non-irradiated. An untreated control will also be irradiated. This design provides built-in controls for the test product (CCP-020 (Diacerein 1%) Topical Ointment) under both irradiated and non-irradiated conditions.

3.3. Study Population

3.3.1. Subject Population

A sufficient number of subjects will be enrolled in order to provide 30 completed subjects evaluable for analysis; an individual subject will be allowed to participate in the study one time only.

A rationale for the choice of sample size is provided in Section 4.2 of this protocol.

3.3.2. Inclusion and Exclusion Criteria

Inclusion Criteria

A subject will be considered eligible for participation in the study if all of the following inclusion criteria are satisfied prior to randomization:

- 1. Is a healthy male or female (to be confirmed by medical history);
- 2. Is 18 years of age or older;
- 3. In the case of a female of childbearing potential, is using two acceptable forms of birth control (oral/implant/injectable/transdermal contraceptives, intrauterine device, condom with spermicide, diaphragm with spermicide, abstinence, partner's vasectomy, tubal ligation). Abstinence or vasectomies are acceptable if the female subject agrees to implement two of the other acceptable methods of birth control if her lifestyle/partner changes;
- 4. In the case of a female of childbearing potential, has a negative urine pregnancy test (UPT) at Day 1 and are willing to submit to a UPT at the end of study (EOS);
- 5. Is free of any systemic or dermatological disorder, which, in the opinion of the Investigator, will interfere with the study results or increase the risk of AEs;
- 6. Has uniformly-colored skin on the lower thoracic area of the back which will allow discernment of erythema, and has Fitzpatrick Skin Types I, II, or III (see Table 1);
- 7. Complete a medical screening procedure; and
- 8. Read, understand, and sign an informed consent.

Exclusion criteria

A subject who has any of the following will be excluded from the study:

- 1. Has a history of photosensitivity or photoallergy;
- 2. Has any visible skin disease at the application site which, in the opinion of the Investigator, will interfere with the evaluation of the test site reaction;
- 3. Is using systemic/topical corticosteroids within 3 weeks prior to and/or during the study, or systemic/topical antihistamines 72 hours prior to and during the study;

- 4. Is not willing to refrain from using systemic/topical anti-inflammatory analgesics such as aspirin (81 mg daily aspirin will be allowed), Aleve, Motrin, Advil, or Nuprin for 72 hours prior to and during the study (occasional use of acetaminophen will be permitted);
- 5. Is taking medication known to cause phototoxic reactions (eg, tetracyclines, thiazides, nonsteroidal anti-inflammatory drugs [NSAIDs]);
- 6. Is using medication which, in the opinion of the Investigator, will interfere with the study results (e.g. anti-inflammatory medications, antipsychotics, anticonvulsants with potential pain relief effects, immunomodulatory medications, and others);
- 7. Is unwilling or unable to refrain from the use of sunscreens, cosmetics, creams, ointments, lotions or similar products on the back during the study;
- 8. Has psoriasis and/or active atopic dermatitis/eczema;
- 9. Has a known sensitivity or allergy to constituents of the materials being evaluated including diacerein, mineral oil, petrolatum, cetyl alcohol, D&C Yellow #10 and/or ethyl paraben;
- 10. Is a female who is pregnant, plans to become pregnant during the study, or is breast feeding a child;
- 11. Has damaged skin in or around the test sites, including sunburn, excessively deep tans, uneven skin tones, tattoos, scars, excessive hair, numerous freckles, or other disfigurations of the test site;
- 12. Has received treatment for any type of internal cancer within 5 years prior to study entry;
- 13. Has a history of, or is currently being treated for skin cancer and/or hepatitis;
- 14. Has a history of, or is currently being treated for diabetes;
- 15. Has any condition that might compromise study results;
- 16. Is currently or expects to sunbathe or use tanning salons during the study;
- 17. Has a history of adverse response (eg, blistering, sun poisoning) to ultraviolet (UV) sun lamps/sunlight exposure;
- 18. Is currently participating in any clinical testing;
- 19. Has any known sensitivity to adhesives; and/or
- 20. Has received any investigational drug(s) within 4 weeks prior to study entry.

3.3.3. Interruption or Discontinuation of Treatment

In accordance with legal requirements and ICH-GCP guidelines, every subject or his/her legal representative has the right to refuse further participation in the study at any time and without providing reasons (see also Section 5.3). A subject's participation is to be terminated immediately upon his/her request. The Investigator should seek to obtain the reason and record this on the case report form (CRF).

If at the time of refusal a study product has already been administered, the subject should be advised on follow-up safety investigations.

If a subject develops a serious adverse event (SAE), his/her termination from the study will be considered by the Investigator. Similarly, if the subject develops conditions over the course of the study which would have excluded his/her entry in the study according to the safety-related medical exclusion criteria, he/she must be withdrawn immediately.

The subject may be withdrawn from the study at any time at the discretion of the Investigator for medical reasons and/or due to non-adherence to the treatment scheme and other duties stipulated in the study protocol. The reasons are to be documented on the CRF.

In addition, the Sponsor retains the right to end the study at any time if the study cannot be carried out as agreed upon in the protocol. In case of premature termination or suspension of the study, the Sponsor's study manager will promptly inform the Investigator/institutions and regulatory authorities of the termination or suspension and the reason for that. It is the responsibility of the Principal Investigator (PI) to notify the Institutional Review Board (IRB) in the case of premature termination/suspension.

3.3.4. Withdrawals

The following medical and other reasons justify a premature termination (by subject or Investigator) of any of the study investigational products (IPs).

- Adverse Event/Serious Adverse Event
- Death
- Protocol Violation (e.g. non-compliance)
- Investigator Judgment
- Pregnancy
- Lost to Follow-up
- Withdrawal by Subject
- Study Terminated by Sponsor
- Other

If a subject withdraws from the study, all efforts will be made to complete a final evaluation, if possible. Subjects discontinued for having experienced an AE will be followed until the AE is resolved, a reasonable explanation is provided for the event, or the subject is referred to his/her own primary medical doctor (PMD). The specific AE in question will be recorded on the appropriate CRF.

3.4. Treatments

3.4.1. Investigational Products and Control

Investigational Product(s):

CCP-020 Topical Ointment

CCP-020 is a topical ointment, 1% (w/w). All excipients used in the topical formulation meet United States Pharmacopeia (USP)/ National Formulary (NF) criteria and are commonly used in

The CCP-020 topical ointment and vehicle ointment will be applied topically, under occlusive patch conditions once over a 4-day period. Each product will be applied to 2 sites (one irradiated site and one non-irradiated site) on the lower thoracic area of each subject's back for approximately 24 (+/- 2) hours. An amount of investigational product sufficient to cover an area of the back approximately 2 cm x 2 cm will be applied (approximately 0.2 mL).

CCP-020 topical ointment and vehicle ointment should be stored at room temperature (15°C/59°F to 30°C/86°F). The PI will be responsible for the suitable storage of the IPs in compliance with the storage instructions and must restrict access to the investigative personnel only.

Lot numbers will be given in the clinical study report.

Manufacturer:

TWi Pharmaceuticals will be responsible for the manufacturing and filling into the primary package; aluminum tubes. TWi Pharmaceuticals will be responsible to package and distribute to TKL. CCP will be responsible for final release of the product. TKL will be responsible for labeling the product upon site delivery.

Control

An untreated irradiated non-occlusive (open) 2 cm x 2 cm site will serve as a control.

3.4.2. Description of Investigational Products

The IPs (CCP-020 [Diacerein 1%] topical ointment and vehicle ointment) will be supplied in aluminum tubes for the clinical study. CCP-020 (Diacerein 1%) topical ointment and vehicle ointment were manufactured and packaged in accordance with good manufacturing practice (GMP).

3.4.3. Description of Patch Conditions

The IP and vehicle will be evaluated under occlusive patch conditions is applied to a 2 cm x 2 cm Webril pad attached to a non-porous, plastic film adhesive bandage (medical tape). The patch is secured with hypoallergenic tape (Micropore), as needed.

3.4.4. Packaging/Labeling

The study medication tube label will show at least the following:

- Protocol number
- Storage conditions
- Instructions for use
- Expiration date
- Sponsor information
- Investigational drug warning
- Space to enter lot number.

A full product description can be found in the Investigator's Brochure (IB).¹

All study IPs should be stored at room temperature (15°C/59°F to 30°C/86°F).

3.4.5. Assignment to Treatment

3.4.5.1. Randomization

Each subject who signs an informed consent and successfully completes the screening procedures will be enrolled in the study. Upon enrollment, each subject will be assigned a unique number, which will correspond to the subject number on the randomization code indicating application placement of the study materials. Each subject in this study will serve as his or her own control.

For each subject, one side of the back will be designated for irradiated sites and the other side will be for non-irradiated sites. On each side one application site will be assigned to the CCP-020 [Diacerein 1%] topical ointment and one will be assigned to the vehicle ointment according to the randomization schedule. On the irradiated side only one additional site will be assigned to the untreated irradiated control.

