3.4.5.2. Blinding

Investigative personnel who are involved in the preparation/application and removal of the treatments (CCP-020 [Diacerein 1%] topical ointment and vehicle ointment) will be unblinded and will not perform the evaluation of skin responses. The trained evaluator who will be evaluating skin responses will be blinded to IPs and the treatment allocation; however, because of the demarcations/skin coloration remaining on the skin following patch removal, complete blinding of the evaluators cannot be completely assured.

Investigative personnel, including the Investigator and the trained evaluator involved in the evaluation of responses, will remain blinded during the course of the study until Database Lock and finalization of the Statistical Analysis Plan (SAP).

In the event of an emergency, if possible, the Investigator or designee will contact the Sponsor with notification of the intent to unblind the treatment codes prior to the actual unblinding. If it is not possible to notify the Sponsor prior to the unblinding, the Investigator or designee will contact the Sponsor immediately following the unblinding procedure and follow with a written notification to document the exact manner in which the code was broken and the justification for the unblinding. The Investigator will communicate the treatment identification to only the investigative personnel who require the information to manage the emergency. Unblinding will happen on site at TKL.

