3.5. Visit Schedule and Assessments

3.5.1. Study Procedures and Visit Schedule

Screening

At Screening, the subjects will receive any necessary written and verbal information, and the informed consent of each subject will be obtained. Demographic data (including Fitzpatrick skin type) will be recorded, a medical history will be taken, and previous and concomitant medications will be reviewed. Eligibility will be determined by review of the inclusion/exclusion criteria.

- Any written and verbal information
- Informed consent
- Demographics
- Previous/concomitant medication
- Review of inclusion and exclusion criteria
- Medical history (including lifestyle and habits)

.

Table 1:	Fitzpatrick Skin Types
Ι	Always burns easily, never tans
II	Always burns easily, tans minimally
III	Burns moderately, tans gradually
IV	Burns minimally, always tans well
V	Rarely burns, tans very well
VI	Never burn, deeply pigmented ^{4,5}

Day 1

On Day 1, all subjects will be questioned regarding the entry criteria and female subjects of childbearing potential will undergo a UPT. If the subject fulfills all the inclusion and none of the exclusion criteria, he/she will be allowed to participate in the study. Concomitant medications and AEs will be reviewed and recorded at this visit.

Upon enrollment, each subject will be assigned a consecutive, unique 3-digit subject number starting with 001, which will correspond to the subject number on the randomization code indicating application placement of the study products.

A baseline evaluation of the patch sites will be performed immediately prior to application of the patches to ensure that no conditions, markings, or coloration of the skin will interfere with interpretation of the study results.

A total of 4 application sites (2 cm x 2 cm each) will be marked on each subject's back, placing 2 sites on opposite sides of the back. Of the 4 sites, 2 will be designated as "irradiated sites" and 2 will be designated as "non-irradiated sites". The CCP-020 [Diacerein 1%] topical ointment and its vehicle ointment will then each be applied to its designated "irradiated site" and its "non-irradiated site" under occlusive conditions. The distance between the patches will be no less than one centimeter. The numbering of the test sites will remain the same throughout the study. The sites will be marked with an indelible, surgical marker.

Minimal Erythema Dose (MED) Determination

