On Day 4, approximately 48 (\pm 4) hours after irradiation (ie, approximately 72 (\pm 4) hours following product application), all application sites and the untreated control site will be evaluated. Adverse events and concomitant medications will be reviewed and recorded, as appropriate. A UPT will be performed for female subjects of childbearing potential.

Retest

Although not all observations of erythema and edema are associated with phototoxicity, erythema and edema must be observed for a reaction to be suspected of being a positive phototoxic reaction. An increase in the intensity of the reaction over time further supports an assessment of phototoxicity. If a reaction is observed at both the irradiated and non-irradiated product sites (ie, if contact sensitization or irritation may have occurred), the reaction upon retest must be at least one grade more intense at the irradiated site than at the non-irradiated site for the reaction to be suspected of being a phototoxicity reaction (refer to Section 3.5.7 for response grades and notations).

If it is determined by the Investigator that a retest should be performed, then the retest patches will be applied as soon as the original reactions have resolved. The Investigator will determine the patch conditions to use during the Retest (see Section 3.4.3). The study material will be applied to naive sites on the back, using appropriate patches to further discriminate a phototoxic reaction from an irritation reaction. Identical patches will be applied to sites previously unexposed to the study material. Approximately 24 (\pm 2) hours later one site will be irradiated with 16 J/cm² of UVA followed by ½ MED of UVB radiation using a filtered light source. An additional untreated site will be irradiated with 16 J/cm² of UVA followed by ½ MED of UVB radiation using a filtered light source. An

be evaluated upon patch removal and approximately 24, 48, and 72 hours after irradiation. Concomitant medications and AEs will also be reviewed.

In some cases the retest may be done on the individual ingredients of the products.

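### The untreated control sits on the irradiated side only, so the evaluator can infer which side had light, leaving two of the six planned contrasts open to expectation bias.

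*Combined protocol and SAP*

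**What the plan says.** All references are to the combined protocol and SAP.

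- **Irradiation goes by side.** Section 3.1: "One side of the back will be designated for irradiation and the other side will remain non-irradiated". Section 3.4.5.1 repeats this for each subject: "one side of the back will be designated for irradiated sites and the other side will be for non-irradiated sites".
- **The control is on one side only.** Section 3.4.5.1: "On the irradiated side only one additional site will be assigned to the untreated irradiated control". Section 3.1 has this site marked on the irradiated side, "which will receive no treatment, but will receive irradiation to serve as an untreated irradiated control". Section 3.4.1 makes it unpatched: "An untreated irradiated non-occlusive (open) 2 cm x 2 cm site will serve as a control". No untreated site is planned on the other side.
- **Marks last.** Section 3.5.1 says of the application sites: "The sites will be marked with an indelible, surgical marker".
- **The control is graded** on Days 2, 3 and 4 (section 3.5.7.1, Table 2).
- **Blinding.** Section 3.4.5.2: "The trained evaluator who will be evaluating skin responses will be blinded to IPs and the treatment allocation". Staff who prepare, apply or remove treatments may not grade. Staff who irradiate are not mentioned. The only limit disclosed is demarcation or colour left by the patch.
- **Outcome and analysis.** The score is a visual erythema grade (0 to 3) plus an edema grade (0 to 2). Sections 4.1 and 4.6.1 analyse the mean of Days 3 and 4 by ANOVA with selected pairwise comparisons.

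**The concern.** A product is phototoxic if it irritates skin after light and does so less, or not at all, without light. The same-product contrast between sides is the plan's direct test of that dependence. The grade is a visual call with no step between no reaction and a mild but definite one. An evaluator who knows which side had light may resolve borderline redness upward there. One who expects a clean product may resolve it downward. Randomising the side would not help, because the extra site identifies it in each subject. In a safety study the downward error is the more troublesome, because a reaction graded as absent gives no reason for a retest.

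**Working it through.** **1. Layout.**

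| Side | CCP-020 | Vehicle | Untreated, open | Total |
|---|---|---|---|---|
| Irradiated | 1 | 1 | 1 | 3 |
| Non-irradiated | 1 | 1 | 0 | 2 |

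The cue is present in every subject, and both analysed readings (Days 3 and 4) come after irradiation.

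**2. Which contrasts cross sides (section 4.6.1).**

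| Contrast | Crosses sides? |
|---|---|
| CCP-020, irradiated v non-irradiated | Yes |
| Vehicle, irradiated v non-irradiated | Yes |
| CCP-020 v vehicle, irradiated side | No |
| CCP-020 v untreated, irradiated side | No |
| Vehicle v untreated, irradiated side | No |
| CCP-020 v vehicle, non-irradiated side | No |

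Two of six depend on even-handed grading across sides. Knowing the side does not favour one site over another within that side. The two product-versus-untreated contrasts carry a separate cue, since the control was never patched.

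**3. How small a shift would register.** The plan gives no alpha, SD, effect size or power, so it has no figure of its own to reproduce. Only n = 30 comes from it (section 4.2). Assume no true effect, all other scores 0, and a false one-grade call at the irradiated site on both days in k subjects. The differences are then k ones and 30 − k zeros:

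- mean = k/30
- SD = √[k(30 − k)/(30 × 29)]
- t = mean/(SD/√30), on 29 df

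k = 4: mean 0.133; SD = √(104/870) = 0.346; SE = 0.0631; t = 2.11; p = 0.043.

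k = 6: mean 0.200; SD = √(144/870) = 0.407; SE = 0.0743; t = 2.69; p = 0.012.

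The result depends on the test:

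- An exact sign test gives 2 × (1/2)^4 = 0.125 for k = 4 and 2 × (1/2)^6 = 0.031 for k = 6.
- If the unspecified ANOVA is a subject-plus-site model over five sites with pooled error, then for k = 4 the error SS = 0.8 × 4 × 26/30 = 2.773 on 4 × 29 = 116 df, MSE = 0.0239, SE = √(2 × 0.0239/30) = 0.0399, t = 3.34 and p = 0.001.

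**4. Bias in either direction.** For a two-sided paired t-test with n = 30 and assumed alpha 0.05, the rejection probability comes from the noncentral t with noncentrality (d/SD)√30, where d is the true difference plus bias. The SDs and bias of 0.2 grade are assumptions.

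| SD of difference | False positives, bias +0.2, true 0 | Power, true 0.4, no bias | Power, true 0.4, bias −0.2 |
|---|---|---|---|
| 0.4 | 75% | above 99% | 75% |
| 0.6 | 42% | 94% | 42% |
| 0.8 | 26% | 75% | 26% |

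The first and last columns agree because d = 0.2 in both.

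**The case against.** The strongest reply has four parts.

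*Safeguards exist.* Section 3.5.7.1 requires a reproducible result on retest before phototoxicity is concluded. Section 3.5.1 requires edema as well as erythema before a reaction is suspected, and treats growing intensity as support. This stands for false positives and rules out saying that the comparison has no protection. It is partial: no masking is described for the retest, and neither safeguard recovers a reaction graded too low.

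*Other comparisons carry weight.* Sections 1 and 4.1 stress comparison with controls, and three contrasts lie wholly on the irradiated side. A general tendency to see redness there would also raise the untreated control score. This stands too. A reader might infer that the whole phototoxicity assessment is unmasked, but the documents support that only for the two cross-side contrasts.

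*Masking of side may be intended.* Side designation sits under the heading on assignment to treatment, so the allocation to which the evaluator is blinded may include it. Section 3.5.1 also keeps site numbering constant, so number-only labels may already be in use. Both are possible. The case report form is not in the documents, so it cannot be said that the control is graded by name. Neither possibility removes the layout cue.

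*The p-values decide nothing.* No alpha or decision rule is stated, and interpretation rests on working criteria and retest. This stands, and the figures are illustrations only.

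A reader might also infer that the one-grade call in step 3 satisfies the retest rule, under which "the reaction upon retest must be at least one grade more intense at the irradiated site than at the non-irradiated site". It does not. That rule applies on retest and when both product sites reacted. In the illustration the non-irradiated site scores 0 and there is no edema.

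**Conclusion.** The masking gap is real but limited. As written, the plan lets the evaluator infer the irradiated side in every subject, does not expressly mask it, does not bar the evaluator from the irradiation, and discloses only a different limit. Two of six contrasts are exposed, in either direction.

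Unmasking is inferred from the layout. The documents do not say that the evaluator knows the side, nor that someone else grades the control. The size and direction of any bias are unknown. Under the stated assumptions, 4 shifted subjects of 30 would be enough for a nominally significant paired t-test (mean difference 0.13, p = 0.043), though not for an exact sign test. A downward bias of 0.2 grade would cut power from 94% to 42% at SD 0.6 and a true difference of 0.4. This merits a low-cost improvement and does not invalidate the study.

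**What to change.** 1. Mark one untreated, open, non-irradiated 2 cm x 2 cm site in the mirror position on the other side, and grade it on Days 2, 3 and 4, so that both sides show the same layout.
2. Identify all sites to the evaluator by number only, if the case report form does not already do so.
3. State in section 3.4.5.2 that the evaluator is blinded to the irradiated side and is not present at irradiation.
4. Disclose there that masking remains imperfect if irradiation visibly changes the skin.

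The cost is one more marked site and one more grade per visit for each subject, a possible label change and a few sentences of text. No subject receives more product or more light. As a by-product, the new site would allow the effect of light alone on untreated skin to be described. The plan does not ask for that, and the case for the change does not depend on it.
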